4. STUDY DESIGN

4.1. Overall Design

This is a Phase 1, parallel group, randomized, open-label, single-dose study to evaluate the PK, safety, and tolerability of IM and IV at different concentrations, doses, routes, and/or sites of administration, in male or female healthy participants aged 18 to 65 years.

The study consists of 3 parts (Part A, an optional Part B, and Part C).

The aim of Part A of this study is to evaluate the safety, tolerability, and relative bioavailability of the 62.5 mg/mL concentration and the new 100 mg/mL concentration of sotrovimab following dorsogluteal injection, as well as the relative bioavailability of the 100 mg/mL concentration at 2 additional IM injection sites, anterolateral thigh, and deltoid.

The aim of Part B of this study, if conducted, is to evaluate the relative bioavailability of 100 mg/mL and/or 62.5 mg/mL IM sotrovimab at up to two injection sites (deltoid, thigh, dorsogluteal, and/or ventrogluteal) relative to the 62.5 mg/mL dorsogluteal arm that is enrolled in Part A, as well as characterize the PK and evaluate the safety of 100 mg/mL sotrovimab at up to two injection sites.

Enrollment will be sequential for Parts A and B, starting with Part A. An IA will be performed once half of the participants in Part A complete at least Day 8. A decision on whether to proceed with Part B will be made by the JSRT and the clinical team after the IA. If the decision is made to proceed with Part B, then Part B of this study will include 1 or 2 treatment arms that would allow for the evaluation of additional injection volumes/number of injections/sites of injections than those evaluated in Part A. The decision about which treatment arms to include in Part B will be informed by tolerability data during part A and clinical considerations. Part B will start enrolling participants once Part A has completed enrollment.

The aim of Part C of this study is to characterize the safety and tolerability of single IV infusion of 3000 mg sotrovimab in Cohort 1 and up to 3000 mg sotrovimab in an optional Cohort 2. Cohort 2 will be opened to potentially assess a different infusion rate and/or dose than Cohort 1. The sotrovimab formulation used in this part will be the 100 mg/mL concentration, which will be diluted as described in the pharmacy manual prior to

administration. Part C is a single IV infusion study, and the enrollment of participants will not be linked to Part A and Part B enrollment.

In Parts A, B and C of the study, all participants will receive a single dose of sotrovimab on Day 1. Additionally, participants in Part A and Part B will need to complete a PRO assessment at home on Day 1, and will also need to complete a PRO assessment at the site on Days 2, 3, 5, and 8.

In all Parts, participants will need to return to the study site on Days 2, 3 and 5 and at Weeks 2, 3, and 4 (Day 29). At Weeks 8, 12, 20, and 24, the participants will need to return to the site or have a home visit. At Week 35, the participants in all Parts will have a phone call visit.

The study duration is 35 weeks after dosing. Participants can be screened up to 28 days before dosing; therefore, the maximum duration a participant will be in the study is 39 weeks.

Part A:

Part A is open-label and participants will be randomized in a 2:2:1:1 ratio to the following 4 treatment arms:

- 500 mg IM of 62.5 mg/mL sotrovimab administered into the dorsogluteal muscles
- 500 mg IM of 100 mg/mL sotrovimab administered into the dorsogluteal muscles
- 500 mg IM of 100 mg/mL sotrovimab administered into the anterolateral thigh muscles
- 500 mg IM of 100 mg/mL sotrovimab administered into the deltoid muscles

Approximately 190 participants will be enrolled assuming a 20% rate of non-evaluable participants to achieve approximately 150 evaluable participants across the 4 treatment arms. Therefore, the randomization ratio of 2:2:1:1 will result in approximately 63 participants randomized to each of the 62.5 mg/mL and 100 mg/mL dorsogluteal arms, respectively, and approximately 32 participants randomized to each of the 100 mg/mL anterolateral thigh and deltoid arms, respectively. Participants will be stratified by sex and 2 BMI strata (18 to \leq 25 and $>$ 25 to 30 kg/m²).

Part B:

Part B is optional and will consist of either 1 or 2 treatment arms (N=32/arm), as described under “Intervention Groups and Duration”.

Approximately 32 participants will be enrolled per treatment arm assuming a 20% rate of non-evaluable participants to achieve approximately 25 evaluable participants within each treatment arm.

If 2 treatment arms are opened in parallel in Part B, then participants will be equally randomized to both treatment arms. However, if only 1 treatment arm is opened for Part B or 2 treatment arms are opened sequentially, then participants will not be randomized. Participants will be enrolled to target a similar representation of sex and BMI groups with those from Part A.

Part B will allow assessment of 500 mg IM dose of 100 mg/mL and/or 62.5 mg/mL sotrovimab administered at the same and/or different injection volume/number of injections/sites of injections than those evaluated in Part A. Potential injection sites to be evaluated in Part B include deltoid, thigh, dorsogluteal, and/or ventrogluteal. An IA will be performed once half of the participants in Part A complete at least Day 8. The selection of treatment arms will be informed by the JSRT and the clinical study team after the IA. Part B will start enrolling participants once Part A has completed enrollment.

Part A and Part B:

The injection volume in the deltoid will not exceed 2.5 mL/injection. The injection volume in the gluteal muscles and thigh will not exceed 5 mL/injection. Follow-up will occur via site and home visits, and a phone call visit (as per the SoA, Section 1.3) for 35 weeks. Part A and Part B participants will receive a single 500 mg dose of sotrovimab for IM injection.

As an exploratory endpoint, this study will assess participant perception of the ISR, including pain (pain-NRS), bothersomeness of ISR, impact on sleep, impact on movement, and acceptability of the ISR (PIN_TS3.0 assessment).

For both Parts A and B, the JSRT will assess ISRs by reviewing data from a sentinel cohort. The sentinel cohort review will occur after all of the treatment arms within a study Part have approximately 5 participants who have completed at least Day 8. During review of the sentinel cohort, the JSRT will make one of the following decisions for each treatment arm:

- to continue enrollment in that treatment arm
- to stop enrollment in that treatment arm
- to have the dose administered using a lower volume of injection for that treatment arm by increasing the number of injections (e.g., 2 injections consisting of 2.5 mL instead of 1 injection consisting of 5 mL)
- to enroll an additional 5 participants in the treatment arm before making a decision.

The JSRT will also review safety data at regular intervals as described in the JSRT charter for both Parts A and B. Refer to Section 10.1.5 for details regarding the JSRT.

Evaluable participants are defined as those who have PK concentration data to allow estimation of the primary endpoints (i.e., AUCD1-29 and Cmax) and inclusion in the analysis.

Part C:

Part C is open-label, and participants will receive single IV infusion. Enough healthy participants will be screened to ensure approximately 200 participants (intend to target up to approximately 20 Japanese participants) are enrolled in Cohort 1 to receive a 3000 mg dose of sotrovimab infused over 60 minutes. Cohort 2 is optional and participants will receive a dose of up to 3000 mg infused over the time period to be specified in the pharmacy manual.

Part C participants will receive study intervention as sotrovimab (100 mg/mL) diluted for IV infusion. Refer to Section 6.1 and pharmacy manual for details. Cohort 1 and optional Cohort 2 enrollment are sequential.

Cohort 1:

- Initial dosing in this cohort will be staggered so that the first 2 participants will be considered sentinels and will be dosed 3000 mg sotrovimab administered intravenously at the same clinical trial site. After at least 24 hours (post dose), and provided the investigator considers the safety and tolerability of the sentinels to be acceptable, the remainder of the participants will be dosed as non-sentinel participants.
- An in-stream safety lead-in data review will occur after approximately 30 participants have completed at least Day 8. JSRT will decide whether to continue with Cohort 1 and whether to proceed with Cohort 2 including the selection of dose and infusion rate. No dosing of further participants will take place until after the review is completed.
- Approximately 170 additional participants will then be enrolled into this cohort.
- An IA, including all data collected, will be conducted after approximately half of the participants in Cohort 1 complete at least Day 15 to support periodic data reviews across the program.

Cohort 2:

- A decision on whether to proceed with Cohort 2 including the selection of dose and infusion rate will be made by the JSRT and the clinical team based on the review of safety lead-in data from Cohort 1.
- Initial dosing in this cohort for the 2 sentinel participants will follow the same procedure as mentioned above in Cohort 1.

The JSRT will also review safety data at regular intervals as described in the JSRT charter for Part C. Refer to Section 10.1.5 for details regarding the JSRT.

Participants in Part C will be enrolled in the study for up to 28 days screening; will receive a single dose of sotrovimab on Day 1 at the study site; will return to the study site on Days 2, 3, and 5 and at Weeks 2, 3, and 4 (Day 29); will also return to the study site or have a home visit at Weeks 8, 12, 20 and 24; and will have an end-of-treatment follow-up period through 35 weeks.

Note: Enrolled means a participant's agreement to participate in a clinical study following completion of the informed consent process and Screening. Potential participants who are screened for the purpose of determining eligibility for the study, but do not participate in the study, are not considered enrolled, unless otherwise specified by the protocol. A participant will be considered enrolled if the informed consent is not withdrawn prior to participating in any study activity after screening.

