2.3.1. Risk Assessment

Potential Risk of Clinical Significance	Summary of Data/Rationale for Risk	Mitigation Strategy
Study Intervention(s): Sotrovimab		

Hypersensitivity reactions (HSRs) reported any time post dose
	
While sotrovimab is a human immunoglobulin G1 (IgG1) mAb, hypersensitivity is a potential general risk associated with the mAb class of therapeutics.
 
Patients who are treated with monoclonal antibodies are at potential risk for developing HSR. This risk may be higher for higher doses or faster infusion rates.
 
In Part C Cohort 1, 3000 mg of the study intervention will be administered over 60 minutes. It is the first time that this particular dose and infusion rate of sotrovimab have been used (refer to IB for further details of sotrovimab dose and infusion time previously used).
 
There was no evidence of systemic infusion reactions in toxicology studies conducted with sotrovimab in monkeys.
 
In COMET-ICE, all HSRs were non-serious, of Grade 1 (mild) or Grade 2 (moderate) severity and reported in 2% of participants who received sotrovimab and in <1% who received placebo (9 participants treated with sotrovimab; 5 participants treated with placebo). None of the reactions in either treatment arm led to pausing or discontinuation of the infusions. All events across both treatment groups were reported as resolved or resolving at the time of DCO.
 
No anaphylaxis events were reported in the COMET-ICE study in participants with mild to moderate COVID-19 not requiring hospitalization at study entry.
 
A potentially life-threatening allergic reaction (anaphylaxis) was observed in 1 adult participant who received sotrovimab in the study of individuals
	
 Participants will be excluded if they have a history of hypersensitivity to any of the constituents present in the investigational product. Participants will be monitored for 1 hour in Part A and Part B. Participants will remain on site for 8 hours post-administration of study intervention for PK assessments. They will also have vitals measured prior to discharge (see SoA in Section 1.3). Investigational product will be administered in the clinic with staff trained in emergency care and resuscitation procedures and emergency care kit on hand during the study intervention administration and post-therapy observation periods. In Part C, initial dosing in Cohort 1 and Cohort 2 will be staggered so that the first 2 participants will be considered sentinels and will be dosed at the same clinical trial site. After at least 24 hours (post dose), and provided the investigator considers the safety and tolerability of the sentinels to be acceptable, the remainder of the participants will be dosed as non-sentinel participants.

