4.2. Scientific Rationale for Study Design

This is a Phase 1 healthy participant study with 3 parts (Part A, an optional Part B, and Part C).

In addition to the current 62.5 mg/mL concentration, a 100 mg/mL ready-to-fill bulk drug substance, leveraging the same formulation, is being pursued in an effort to lower the injection volume when injected intramuscularly. This will allow additional injection sites to be used. The 100 mg/mL concentration is also being studied as an IV infusion.

Part A and an optional Part B of this study are open-label, parallel group, randomized parts, which will evaluate the safety, tolerability, and relative bioavailability of the 62.5 mg/mL concentration and the new 100 mg/mL concentration of sotrovimab following IM injections at different sites. Part A and Part B participants will receive a single 500 mg dose of sotrovimab for IM injection.

Part C is an open-label, single IV infusion study, which will characterize the safety and tolerability of 3000 mg sotrovimab in Cohort 1 and up to 3000 mg sotrovimab in an optional Cohort 2. Cohort 2 will be opened to potentially assess a different infusion rate and/or dose than Cohort 1.

Part A and Part B

An open-label design is chosen as the injections are given at different sites and different number of injections may be used. Given the open-label design, investigators, site study staff, and participants will not be blinded.

BMI and sex are principal determinants of parenterally administered mAb exposure. Therefore, in Part A, randomization to treatment arms will be stratified by sex and BMI to aim for a balance of strata between treatment arms. In Part B, participants will be enrolled to target similar representation of BMI and sex groups as in Part A.

The number of participants randomized to each treatment arm will provide acceptable precision for estimation of relative bioavailability. Due to the extended $t_{1/2}$ of sotrovimab, 24 weeks is expected to provide sufficient duration to ensure the extrapolated portion of the AUC will be less than 20%.

Part C

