9.4. Interim Analysis

Part A and B:

In Part A and B, safety and tolerability data aggregated by treatment arm will be reviewed in-stream by the JSRT (see Section 10.1.5). A planned sentinel review will be conducted after approximately 5 participants per treatment arm complete at least Day 8 visit as described in Section 4.1.

Data from JSRT reviews may be used to inform study conduct or wider program decisions. These data will not be fully cleaned or undergo formal statistical analysis.

An IA will be conducted to review Part A data after approximately half of the participants in Part A complete at least Day 8 visit. The purpose of this interim is to inform the decision on whether to open Part B, and if needed the selection of treatment arms; further details of this IA will be specified in the SAP. Recruitment into Part A will continue with no pause at the time of the interim.

Thereafter, participants will continue to complete the remaining schedule of assessments as per the protocol.

Part C:

In Part C, aggregated safety and tolerability data will be reviewed in-stream by the JSRT (see Section 10.1.5). A planned in-stream review of safety lead-in data from Cohort 1 will be conducted after approximately 30 participants complete at least Day 8 visit as described in Section 4.1. The purpose of this review is to inform the decision to continue with Cohort 1 and whether to proceed with Cohort 2 including the selection of dose and infusion rate made by the JSRT and the clinical team. No dosing of further participants will take place until after the review is completed.

Data from JSRT reviews may be used to inform study conduct or wider program decisions. These data will not be fully cleaned or undergo formal statistical analysis.

An IA, including all data collected, will be conducted after approximately half of the participants in Cohort 1 complete at least Day 15, to support periodic data reviews across the program. Further details of this IA will be specified in the SAP.

Thereafter, participants will continue to complete the remaining schedule of assessments as per the protocol.

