10.1.5. Committees Structure

10.1.5.1. Joint Safety Review Team

A JSRT comprised of team members from clinical research, global safety, and statistics from GSK and Vir, will review safety data throughout the study from all participants. The responsibilities of the JSRT and frequency of assessments will be outlined in the JSRT charter. The JSRT will review safety data from a sentinel cohort for each study Part and will review Part A data to inform Part B decisions, as described in Section 4.1.

Additionally, the JSRT will review safety lead-in data from Part C Cohort 1 to decide to continue with Cohort 1 and whether to proceed with Cohort 2 (with a selection of different dose and infusion rate than Cohort 1). JSRT may request additional data before making a decision.

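### If optional Cohort 2 infuses faster than Cohort 1, its only written dosing hold is two sentinels for 24 hours; a JSRT Day 8 hold would be a cheap addition

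*Protocol*

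**What the plan says.** **Cohort 1.** Protocol Section 4.1 sets two cohort-level holds for 3000 mg over 60 minutes. The first is two sentinels at one site. The rest are dosed after at least 24 hours, "provided the investigator considers the safety and tolerability of the sentinels to be acceptable". The second is a JSRT review once about 30 participants have completed at least Day 8: "No dosing of further participants will take place until after the review is completed". Section 9.4 repeats this and ties it to the cohort: "A planned in-stream review of safety lead-in data from Cohort 1 will be conducted after approximately 30 participants complete at least Day 8 visit".

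**Cohort 2.** Section 4.2 gives its purpose: "Cohort 2 will be opened to potentially assess a different infusion rate and/or dose than Cohort 1". The dose is capped at 3000 mg. No limit on rate is stated, and Table 3 leaves dose and infusion time to the pharmacy manual. The JSRT and the clinical team decide whether to open it, and at what dose and rate, from the Cohort 1 lead-in. On holds, Section 4.1 says only: "Initial dosing in this cohort for the 2 sentinel participants will follow the same procedure as mentioned above in Cohort 1".

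**Elsewhere.** In Parts A and B the JSRT reviews ISRs once all arms "have approximately 5 participants who have completed at least Day 8"; no dosing hold is stated there. Section 10.1.5.1 says "The JSRT will review safety data from a sentinel cohort for each study Part" and refers to Section 4.1 for the description. Section 2.3.1 says that faster or shorter infusion may raise the risk of hypersensitivity and infusion-related reactions. Of Cohort 1 it says: "It is the first time that this particular dose and infusion rate of sotrovimab have been used".

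**The concern.** The protocol names infusion rate as a possible risk factor, lets Cohort 2 change it, and caps the dose but not the rate. All Cohort 1 data are planned at 60 minutes, so they bear on the dose but do not directly test a faster infusion. If Cohort 2 is faster, the decision to go beyond two participants is the investigator's, after as little as 24 hours. The team that held Cohort 1 at about 30 participants has no written hold in Cohort 2. These are healthy volunteers, and Section 2.3.2 states that no direct benefit to them is currently known.

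**Working it through.** **1. The plan's own figures.** Section 9.5 gives a 90% chance of at least one event, using 1 − (1 − p)^n.
- Cohort 1: n = 200, p = 1.14%: 1 − 0.9886^200 = 89.9%.
- Cohort 2: n = 50, p = 4.5%: 1 − 0.955^50 = 90.0%.

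Both reproduce.

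**2. Cohort 1 rate.** 3000 mg / 60 min = 50 mg/min. The documents do not print this figure. At 3000 mg, any shorter infusion exceeds it: for example, 45 minutes gives 66.7 mg/min and 30 minutes gives 100 mg/min (these times are assumptions).

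**3. Cohort-level holds in the visible protocol.**

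| | Cohort 1 (about 200) | Cohort 2 (about 50) |
|---|---|---|
| Two sentinels, at least 24 h, investigator releases | Yes | Yes |
| JSRT Day 8 review with dosing stopped | Yes, at about 30 (30/200 = 15%) | None written |
| Can follow after the last written hold | About 170 | 50 − 2 = 48 |

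The synopsis, Section 2.3.1, Section 4.1, Section 9.4 and Section 10.1.5.1 all attach the lead-in to Cohort 1. SAP Section 4.6 mentions it for Part C without naming a cohort, but defers to the protocol, and that SAP covers only Cohort 1. Section 10.1.5.1 does not fill the gap: it states no hold, and Section 4.1 describes a JSRT sentinel review only for Parts A and B.

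**4. What 2 or 10 participants can show.** The 1.14% is the infusion-reaction rate that Section 9.5 quotes from COMET-ICE. The 5%, 10% and 20% rates are assumptions for scale. P(at least 2) = 1 − (1 − p)^n − n·p·(1 − p)^(n−1). For n = 10 and p = 10% this is 1 − 0.349 − 0.387 = 0.264.

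| True rate | At least 1 in 2 | At least 1 in 10 | At least 2 in 2 | At least 2 in 10 |
|---|---|---|---|---|
| 1.14% | 2.3% | 10.8% | 0.01% | 0.6% |
| 5% | 9.8% | 40.1% | 0.25% | 8.6% |
| 10% | 19.0% | 65.1% | 1.0% | 26.4% |
| 20% | 36.0% | 89.3% | 4.0% | 62.4% |

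One reaction would not by itself stop the cohort, so the last two columns matter more.

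**5. If no reaction is seen.** The upper limit of the two-sided 95% exact interval is 1 − 0.025^(1/n): 84.2% for n = 2, 30.8% for n = 10, and 11.6% for n = 30 (the Cohort 1 lead-in).

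**6. Size of the hold.** Proportional scaling of the Cohort 1 lead-in gives (30/200) × 50 = 7.5, about 8. With 8, the chance of two or more reactions at 10% is 1 − 0.430 − 0.383 = 0.187, about 19%. Ten is a round number slightly above that, chosen by judgement.

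**The case against.** The strongest reply is that Cohort 2 does not start from nothing.
- Its dose cannot exceed 3000 mg, and enrollment is sequential, so it follows Cohort 1 experience at 3000 mg: about 200 participants on a plain reading, and at least the 30-participant Day 8 review on the earliest one.
- The JSRT and clinical team choose its dose and rate, and the JSRT reviews safety data regularly.
- Section 2.3.1 lets the investigator or sponsor extend the infusion time. Infusions are paused at a Grade 2 infusion-related reaction and stopped at Grade 3 or higher.
- Cohort 2 is optional and might be slower or at a lower dose. SAP Section 1 says that it was not confirmed and would need a SAP amendment.
- Infusion-related reactions are counted within 24 hours, which the sentinel window already covers.

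Most of this stands. A reader might infer that a faster Cohort 2 would be in the same position as Cohort 1's first use. The documents do not support that: Cohort 1 was new in both dose and rate, whereas Cohort 2 can go beyond it only in rate. Whether faster rates have been used before cannot be judged here, because Section 2.3.1 refers to the investigator's brochure. Nor is there a stated rule that first use requires a JSRT hold; Cohort 1 is a single instance, and limiting the lead-in to it may have been deliberate.

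What the reply does not remove is narrower. None of these safeguards directly tests the faster rate before most of the cohort is dosed. The pause and stop rules protect the participant being infused, and extending the infusion is discretionary; none of them holds the next participant. For infusion-related reactions, the gain from a hold is more participants and a JSRT judgement, not a longer window. Hypersensitivity is counted at any time post dose, so Day 8 adds something there.

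**Conclusion.** The point holds as a conditional, cheap improvement. If Cohort 2 opens at more than 50 mg/min, the visible protocol lets 48 of 50 healthy volunteers follow two sentinels on the investigator's judgement. A hold at 10 raises the chance of seeing two or more reactions from 1% to 26% at a 10% true rate, and from 4% to 62% at 20%. If the faster rate adds no risk, the hold will rarely show anything: at 1.14%, two or more in 10 has a chance of 0.6%.

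The conclusion depends on Cohort 2 opening with a faster rate, which the documents permit but do not state. It covers only the visible protocol: the JSRT charter and pharmacy manual were not available, the Part C figures are missing, and a hold may already exist there. At 50 mg/min or slower, the concern largely falls away. It should not be read as saying that Cohort 2 lacks JSRT oversight.

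**What to change.** In Protocol Section 4.1 (Cohort 2) and Section 9.4, add:

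> If the Cohort 2 infusion rate exceeds that of Cohort 1 (50 mg/min), no further participants will be dosed after approximately the first 10 participants until the JSRT has reviewed their safety data through at least Day 8 and decided whether to continue.

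This reuses a mechanism already in place for Cohort 1 and, like it, leaves the decision to the JSRT without a numerical threshold. If the charter already contains such a hold, copying it into Section 4.1 is enough.

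The cost is a pause of about 8 days plus review time, only if a faster rate is chosen, and a protocol amendment. Under Section 10.1.1 the amendment needs IRB/IEC approval, and health authority approval if substantial. No extra participants, visits or samples are needed.
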